The use of Omega-3FA in an adolescent and young adult prodromal population is novel. Therefore the level of risk is considered moderate. Although this study is greater than minimal risk, it offers subjects direct benefit from participation because of the Omega-3FA and placebo treatments. It is also possible that the concurrent use of Omega-3FA will improve metabolic indices in all subjects. Because Omega-3FA is not

specifically approved by the FDA for use in early psychosis, we have received a certificate for an Investigational New Drug (IND) for the current Research Plan.

The sample of 128 prodromal subjects will be recruited from 8 sites over 16 months. The active treatment phase will be completed within 6 months, with 12-, 18-, and 24-month follow-ups. Each site will obtain institutional review board approval of the protocol. The UCLA site, directed by [name], and the UCSD site, directed by [name], coordinate the trial, with responsibility for acquisition of the Omega-3 and placebo pills, group assignments, and data analysis.

Sample

Adult subjects must give written informed consent, and minors must give written informed assent with consent from a parent or guardian.

Inclusion Criteria: Subjects will be included if they are treatment-seeking patients between the ages of 12 and 30 who meet diagnostic criteria for a possible prodromal syndrome and are part of the ongoing NAPLS study at each site. The enrollment targets for each site are based on enrollment into the parent NAPLS study over the past 12 months, after projecting a 50% refusal rate for participation in the clinical trial: 20 from UCLA, 20 from Emory, 10 from Harvard, 16 from Zucker Hillside Hospital, 12 from UNC, 14 from UCSD, 22 from Calgary, and 14 from Yale. In total, 128 subjects from all of the participating sites will be randomized into drug versus placebo in the Omega-3 long chain fatty acid (Omega-3FA) study. All subjects will receive clinical assessment, fluid sampling, and adverse event monitoring during the 6-month trial.

Exclusion Criteria: Subjects will be excluded for any of the following reasons:

- (1) use of antipsychotic medication in the previous month.
- (2) concomitant medical or neurological illness.
- (3) history of significant head injury.
- (4) alcohol or drug abuse (excluding nicotine) in the past month or dependence in the past three months.
- (5) screening full scale estimated IQ < 80.
- (6) active suicidal or homicidal ideation.
- (7) pregnancy or lactation.

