Background Diet: Baseline diet characterization will be assessed using a systematic checklist. We considered using an open-ended diary that requires recording of all food intake, but it seems unlikely that adolescents with early psychosis symptoms would comply to a satisfactory degree. The checklist is easy to complete and is more likely to be accurate than unstructured self-reports. The list includes foods that are rich in Omega-3FA. It will be given to the family at the first screening visit, and will be collected for the two consecutive weeks preceding entry into the treatment phase. Intake will be categorized as low (0-1 serving/wk of Omega-3FA rich diet), intermediate (2-3 servings/wk), or high (4 or more servings/wk). In addition fasting erythrocyte FA composition will be assessed to use as another means of controlling for background diet at baseline.

Laboratory and Metabolic Measures: After confirming eligibility for the study, a urine sample will be taken for a drug screen, and a serum pregnancy test on females. Fasting erythrocyte FA composition will be quantified at baseline, month 3 and month 6 using capillary gas chromatography. The ratio of Omega-6 to 3FAs will be used to index pretreatment vs posttreatment FA composition as an objective measure of treatment adherence, to assess for dietary differences between subjects and assure that subjects on placebo are not taking Omega-3FA supplementation from an outside source. Thiobarbituric Acid Reactive Substances (TBARS) will be used for screening and monitoring lipid peroxidation before and after the treatment trial. In addition, to assess metabolic parameters, baseline measures of fasting glucose and lipids, weight, abdominal girth and blood pressure will be obtained and repeated at the end of the trial.

Table 1. Study Procedures and Timeline

Visit	1	2	3	4	5	6	7	8	9	10	11	Other
Day	-7 to -1	1	30 (+/-2d)	60 (+/-5d)	90 (+/-5d)	120 (+/-5d)	150 (+/-5d)	180 (+/-5d)	360 (+/-15d)	540 (+/-15d)	720 (+/-15d)	
Month		0	1	2	3	4	5	6	12	18	24	
Screening												
Informed consent	X											
Inclusion/exclusion	X											
Characterization												
Medical history	X											
Demographics		X										
FIGS		X										
PAS		X										
Treatment												
Randomization		X										
Capsule dispensing	X	X	X	X	X	X	X					
Pill count		X	X	X	X	X	X	X				
Psychosocial												
Up to 6 sessions of supportive case management												
Safety/Physical												
Physical exam	X											

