Continuation Therapy: Although we considered forbidding patients to use Omega-3FAs after the 6-month active treatment phase, we determined that doing so would be impractical and potentially damaging to the parent study, because patients and families convinced of the benefits of Omega-3FAs would likely drop out at that point. For this reason, we will suggest but not enforce discontinuation, and of course, no “pills” will be provided by the study after the active treatment phase. We will, however, continue to record dietary and supplemental sources of Omega-3FAs for the full two-year follow-up.

Potential for Interference with Aims of Parent Grant: The aims of the parent NAPLS grant (elucidating predictors and mechanisms of conversion to psychosis) would be undercut if we were to implement a treatment program that was effective in eliminating conversions. However, neither FFT nor Omega-3 FAs are expected to have the potency to prevent psychosis in all individuals. At the same time, given that prodromal patients are distressed and treatment seeking, these individuals are getting treatments in the community regardless of their participation in our study. Such community-based treatments are not structured and lack control conditions. The large sample size target for the parent study (720 prodromal patients followed longitudinally) was proposed in part to take variability in exposure to such treatments into account. Since the parent grant was funded, we have had the opportunity to implement one clinical trial (FFT study) and possibly a second one (Omega-3). The primary advantages of implementing such controlled treatment trials within the context of the NAPLS study are that we can estimate conversion risks in the patients who received more intensive or active interventions compared with those who received less intensive or inactive treatments, we can determine if predictors of conversion differ according to the type or degree of interventions received, and we can test whether effectiveness of interventions is mediated by changes in neural, hormonal, and other processes being assessed in the core NAPLS study.

Study Management: Prior to study launch, study investigators and other key personnel will participate in several conference calls to provide training on study procedures, including recruitment strategies, inclusion and exclusion criteria, use of rating scales, and data management procedures.

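### The plan neither excludes patients already taking omega-3 supplements nor says how they are identified and handled in the analysis

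*Combined protocol and SAP*

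**What the plan says.** - **Eligibility.** The list under Sample, Exclusion Criteria opens "Subjects will be excluded for any of the following reasons" and gives seven items. One is "use of antipsychotic medication in the previous month". None mentions omega-3 or fish-oil supplements. The protocol states no washout, no baseline fatty-acid threshold and no explicit ban on outside supplements during the six months.
- **Diet.** Under Procedures, Background Diet, the checklist is described as covering omega-3-rich foods, scored in servings per week. Supplements are not mentioned. Baseline erythrocyte composition is to serve as a further control for background diet.
- **Assay.** Under Laboratory and Metabolic Measures: "Fasting erythrocyte FA composition will be quantified at baseline, month 3 and month 6 using capillary gas chromatography". On its use: "The ratio of Omega-6 to 3FAs will be used to index pretreatment vs posttreatment FA composition as an objective measure of treatment adherence". The sentence then adds two more purposes: to compare diet from one subject to another, and to "assure that subjects on placebo are not taking Omega-3FA supplementation from an outside source".
- **Other records.** All concomitant treatment is recorded. Table 1 schedules treatment logs at all 11 visits. Continuation Therapy says that recording of dietary and supplemental omega-3 sources will continue through the two-year follow-up.
- **Analysis.** Power Calculations and Statistical Analyses gives Cox and Kaplan-Meier methods for time to conversion and mixed models for the other outcomes. The baseline covariates offered as examples for the mixed models are symptom severity, age and gender.

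**The concern.** The primary question is whether omega-3 lowers conversion compared with placebo. A placebo patient already on a supplement may be partly or fully treated, and an active-arm patient already on one receives only an increment. Both shrink the difference that the trial is trying to detect.

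The sponsor sees outside use as a threat, because the assay is given the job of ruling it out in the placebo arm. Other background treatments are handled explicitly: recent antipsychotic use is an exclusion and antidepressant status is a stratification factor. The test substance itself gets neither.

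If outside use is judged on change in the ratio, a placebo patient with stable use shows about no change and looks like an uncontaminated patient. An active-arm patient with prior use may show a blunted change and look non-adherent.

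**Working it through.** **Step 1: what each element does for a patient with stable prior use.**

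| Element | Can it show prior use? | Rule attached |
|---|---|---|
| Exclusion criteria | Not asked | None |
| Food checklist | Not as described (foods only) | Low, intermediate or high intake |
| Change in ratio, before vs after | No; change is near zero on placebo | None |
| Absolute ratio at baseline, months 3 and 6 | Yes, it should be low throughout, but it cannot separate supplements from a fish-rich diet | None |
| Treatment logs and supplement records | Probably; log content before month 6 is not spelled out | None |
| Primary Cox model | No fatty-acid or supplement term named | None |

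The information is largely collected. What is missing is a decision at entry and a rule for using the information afterwards.

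**Step 2: the plan's own power figure.** Inputs from the power section: 128 randomised, 20% attrition, about 51 completers per arm, 12-month conversion 22% on placebo and 4.5% on omega-3, alpha 0.05. Sidedness is not stated; two-sided is assumed here.

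- Arcsine method: h = 2·asin(√0.22) − 2·asin(√0.045) = 0.549. Power = Φ(0.549·√(51/2) − 1.96) = 79.2%, which matches the stated 80%.
- Unpooled two-proportion method: SE = √[(0.22·0.78 + 0.045·0.955)/51] = 0.0649. z = 0.175/0.0649 = 2.70. Power = Φ(2.70 − 1.96) = 77%.

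**Step 3: illustrative dilution.** The documents give no prevalence of prior use, so the share q is an assumption, equal in both arms. Suppose users on placebo carry the full treated risk. The placebo rate becomes (1 − q)·0.22 + q·0.045, and the active rate stays at 4.5%.

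| q | Placebo rate | Risk ratio | Power, two-proportion | Power, arcsine |
|---|---|---|---|---|
| 0% | 22.0% | 4.9 | 77% | 79% |
| 5% | 21.1% | 4.7 | 74% | 76% |
| 10% | 20.3% | 4.5 | 70% | 72% |
| 20% | 18.5% | 4.1 | 62% | 64% |

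**Step 4: how far this depends on the assumptions.**

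- *Partial benefit.* If prior use gives half the benefit, a user's placebo-arm risk is (0.22 + 0.045)/2 = 13.25%. At q = 20% the placebo rate is 0.8·0.22 + 0.2·0.1325 = 20.3%, and two-proportion power is 70% instead of 62%.
- *Base rate already includes users.* The 22% was observed in an earlier cohort receiving various community treatments. If that cohort had a similar share of users, the 22% needs no lowering and this calculation shows no loss against the planned figure.
- *A different mechanism.* If users instead kept the 22% risk in both arms (no added benefit from the study capsules), the active rate at q = 10% would be 0.9·0.045 + 0.1·0.22 = 6.25% and arcsine power 66%. Nothing in the documents favours this case; it shows that the direction is firmer than the size.

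**The case against.** The strongest reply is that the protocol already measures what is needed. Absolute erythrocyte composition is obtained before treatment and twice during it. The ratio is meant to compare subjects as well as to track change. Concomitant treatment is logged at every visit, and supplemental sources are recorded. A reader might infer from the before/after wording that prior use cannot be seen, or that the ratio is the only safeguard. The documents support neither inference.

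A reader might also take the remark that "patients and families convinced of the benefits of Omega-3FAs would likely drop out at that point" as evidence that prior use is common here. That remark explains why omega-3 use is not forbidden after the six-month treatment phase, and it says nothing about use before screening.

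Third, testing a fixed dose on top of measured background intake is a legitimate design, and the protocol treats diet that way, keeping patients with high intake. Excluding supplement users would leave dietary omega-3 in place. This stands as a reason to offer the sponsor an alternative to exclusion.

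Another part of the reply fails. Collecting data that could reveal prior use does not settle how it will be used: no threshold, action or analysis term is given, and the stated intention to control for background diet does not reach the statistical section.

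**Conclusion.** The point holds as a gap in both eligibility and analysis. The protocol sets out to keep outside omega-3 out of the placebo arm, yet it admits patients already taking supplements and does not say how they will be identified or handled.

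The harm is loss of contrast and power. Confounding is a tempting stronger reading, but randomisation should balance prior use on average. It would also go too far to say that a null result could never be told apart from contamination: the three absolute ratios and the treatment records would allow a check, although none is pre-specified. Pill counts at Visits 2 to 8 likewise give a second view of adherence.

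The size cannot be fixed from the documents. The fall from about 77% to 74–62% assumes 5% to 20% users, full benefit in those users, and a 22% base rate free of users. Relaxing either of the last two reduces the loss. The power section already concedes less than 80% power for effects smaller than the one assumed, so a cheap protection of the contrast is worth having.

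**What to change.** 1. **Eligibility.** Add to the Exclusion Criteria regular omega-3 supplement use within a fixed look-back before randomisation, with the length set by the sponsor, and ask about it at Visit 1 alongside the food checklist. Cost: one line and one question, with a few candidates lost or delayed.
2. **Detection.** In Laboratory and Metabolic Measures, state that outside supplementation is judged on the absolute ratio at baseline, month 3 and month 6 together with recorded supplement use, not on change alone. Give the cut-off in advance, and state that treatment logs capture supplements from Visit 1. The assays are already planned.
3. **If the sponsor prefers not to exclude.** In the statistical section, pre-specify a supportive primary analysis omitting patients with baseline supplement use, or a Cox model adjusted for the baseline ratio. Both use pre-randomisation information, so the randomised comparison is preserved. Month 3 and month 6 values should not define who is omitted, because treatment affects them. Cost: omission reduces the sample. With about 51·(0.22 + 0.045) = 13.5 expected events among completers, the adjusted model should carry the baseline ratio as a single term.

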Procedures

During the week prior to randomization and beginning study capsules, patients will undergo eligibility and baseline examinations. After beginning study capsules, patients will be scheduled for 6 monthly follow-up visits as well as 12-, 18-, and 24-month follow-ups (Table 1).

Omega-3FA and Placebo: The Omega-3FA compound will be manufactured by Ocean Nutrition Canada and contain an 2:1 proportion of EPA to DHA in which each capsule includes 370 mg EPA and 200 mg DHA as well as 2 mg/g Tocopherol. The dose will be two capsules per day for a total of 740 mg of EPA and 400 mg of DHA. The ratio and dose of Omega-3FA were selected based on previous data from controlled trials that demonstrates the efficacy of EPA in trials with schizophrenia patients^{37, 38} and the potential benefit of a low dose of DHA in combination with EPA per the Amminger study⁶⁰ in prodromal patients. The placebo is a soybean/corn blend. Both the Omega-3FA and placebo are colored with carob (so shell is brown) and flavored with natural lemon-lime, to mask them. Certificates of analysis for the Omega-3FA and placebo compounds are included in the Appendix. Ongoing testing by independent laboratories will assure the levels of Omega-3FA in capsules, stability, and absence of any contaminants, including toxic substances in this product. Stability and toxicology testing will be provided by Siliker Canada Co. UCLA will receive the compounds and assign coded numbers to packets before distribution to sites and thereby administer the double blind design.

Antipsychotics: Prodromal patients currently on anti-psychotic medication will be excluded from the study. It is possible that prodromal subjects will develop worsening symptoms and require such treatments during the course of the trial, which is allowed. All concomitant treatment will be recorded.

Antidepressants: Prodromal patients currently on anti-depressant medication will be included in the study; randomization to Omega-3FA vs placebo will be stratified on anti-depressant medication status.

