Vital signs & weight	X		X	X	X	X	X	X	X	X	X	
Labs (LFTs etc)	X				X			X				
Adverse events	X	X	X	X	X	X	X	X				
Treatment Logs	X	X	X	X	X	X	X	X	X	X	X	
Clinical Outcomes												
SOPs		X	X	X	X	X	X	X	X	X	X	
SCID		X							X	X	X	
SCID-SPD		X							X	X	X	
Depression (CDSS)	X	X	X	X	X	X	X	X	X	X	X	
GAF	X	X	X	X	X	X	X	X	X	X	X	
GF-Social	X	X	X	X	X	X	X	X	X	X	X	
GF-Role	X	X	X	X	X	X	X	X	X	X	X	
Other Outcomes												
Neuropsychology		X						X	X		X	
Brain imaging		X						X	X		X	
Electrophysiology		X						X	X		X	
Salivary cortisol		X							X		X	
DNA/RNA/plasma		X							X		X	

Key: X=Existing Protocol; X=Added for Omega3 Trial

Concomitant Medications: Subjects may continue doses of antidepressant, mood stabilizer, or stimulant medication as prescribed independently of their participation in this trial. Antipsychotic medication will not be permitted unless subjects develop worsening symptoms and require antipsychotic medication during the course of the trial. All concomitant treatment will be recorded.

Concomitant Psychotherapy: During the 6-month active treatment phase, all subjects will receive up to 6 sessions of supportive case management, as needed, as part of their evaluations by psychological staff. Staff members will provide support and address the young person's efforts to cope with symptoms and functional deficits. In addition, subjects will be permitted to participate in any outside of study supportive psychotherapy, with all concomitant psychological treatments recorded.

Family Focused Treatment (FFT) Study: Patients enrolled in the FFT study will be stratified prior to randomization in the Omega-3 trial, such that equal numbers of FFT participants will be assigned to the Omega-3FA and placebo groups. About one-quarter of the patients enrolled in NAPLS participate in the FFT study. Because the enrollment period for the FFT study will end on December 31, 2011, only about one-third of the participants in the Omega-3 trial would actually be eligible to participate in both studies. Thus, the overlap between patients participating in the FFT and Omega-3 trials is expected to be less than 10% (i.e., .33 x .25 = .083). Given this, we do not expect to have sufficient numbers of cases enrolled in both studies to be able to test whether participation in one moderates effects of participating in the other, but stratified group assignment

will ensure that equal numbers of cases in active treatment and control conditions are balanced for FFT participation.

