For evaluation of the primary outcome measure (time to conversion), we will use Cox's proportional hazards model and Kaplan-Meier survival analysis as implemented in SAS PROC PHREG and LIFETEST. The secondary and tertiary outcome variables, all treated as continuous variables, will be examined as a function of treatment condition and site using mixed effects regression models. Mixed effects models permit the estimation of symptom trajectories at the level of the individual participant over time. Then the random coefficients from these within-participant trajectories are modeled as a function of treatment condition and appropriate baseline covariates (e.g., initial severity of symptoms; age or gender). At the level of the individual participant, time-varying covariates (e.g., antipsychotic treatment or not) can also be controlled, thus permitting the estimation of within-participant trajectories over and above any time-varying covariates. Similar approaches will be used to examine the trajectory of functional outcome scores. The advantages of mixed effects models over traditional repeated measures models are that they allow for (1) the inclusion of participants with missing data, (2) observations that are unequally spread out over time (both within and between participants), and (3) more flexible modeling of variance and covariance patterns of residuals. We will use two programs – SAS PROC MIXED and MIXREG – to examine these models.

Human Subjects

Only participants who meet eligibility criteria for and have previously been consented for the North American Prodrome Longitudinal Study (NAPLS) will be invited to participate. Participants will thus include individuals who are referred or respond to announcements because they may be experiencing symptoms that are associated with the prodrome of psychosis. These individuals will be referred by community health care providers or will be self-referred in response to media announcements or internet searches. Recruitment involves providing announcements to local primary care practitioners, including community pediatricians, family practice physicians, local clergy, educators, clinical social workers, psychologists, and psychiatrists. This information will include a letter introducing the study, and a brochure that describes prodromal symptoms.

Based on enrollment in NAPLS to date, about 65% of the sample are expected to be males. About 20% of subjects are expected to be African American and about 10% Latino.

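### The main secondary and tertiary models should compare assigned arms and include both randomisation strata; adjustment for on-study antipsychotics should be a labelled sensitivity analysis

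*Combined protocol and SAP*

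**What the plan says.** One paragraph in Power Calculations and Statistical Analyses covers the secondary outcome (SOPS total) and the tertiary outcomes (social and role functioning). Its firm commitment is that they "will be examined as a function of treatment condition and site using mixed effects regression models". The trajectory coefficients are then "modeled as a function of treatment condition and appropriate baseline covariates (e.g., initial severity of symptoms; age or gender", so the baseline covariates are given only by example. On variables that change during follow-up it says "At the level of the individual participant, time-varying covariates (e.g., antipsychotic treatment or not) can also be controlled", and adds that trajectories can then be estimated net of them.

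Other sections bear on this:

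- **Hypotheses** frames both sets of outcomes as change from baseline at 6 and 12 months, compared by random assignment.
- **Exclusion Criteria** rules out antipsychotic use in the month before entry.
- **Procedures, Antipsychotics:** "It is possible that prodromal subjects will develop worsening symptoms and require such treatments during the course of the trial, which is allowed".
- **Concomitant Medications:** "Antipsychotic medication will not be permitted unless subjects develop worsening symptoms and require antipsychotic medication during the course of the trial".
- **Procedures, Antidepressants:** "randomization to Omega-3FA vs placebo will be stratified on anti-depressant medication status".
- **Family Focused Treatment (FFT) Study:** "Patients enrolled in the FFT study will be stratified prior to randomization in the Omega-3 trial", with the note that "the overlap between patients participating in the FFT and Omega-3 trials is expected to be less than 10% (i.e., .33 x .25 = .083".

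**The concern.** Two things are left open.

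First, starting an antipsychotic is a response to worsening symptoms, and symptom severity is what the SOPS measures. If Omega-3 affects symptoms, it can affect who starts. The Background section itself describes a trial in initially unmedicated patients in which all 12 on placebo, but only 8 of 14 on EPA, were taking antipsychotics at the end. Those patients had schizophrenia, so the rates do not carry over, but an arm difference in starts is plausible. Conditioning on such a variable breaks the randomised comparison. It can remove part of the treatment effect, or add back what antipsychotics took away. With neither model labelled as the main one, the choice could be made after the data are seen.

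Second, allocation is stratified on two factors that no model names. Leaving them out mainly costs precision.

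**Working it through.** **1. What is fixed and what is open**

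| Item | Status in the analysis text |
|---|---|
| Treatment, site | committed |
| Initial severity, age, gender | examples |
| Antidepressant status, FFT participation | not named |
| On-study antipsychotic use | permitted, role not stated |

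**2. The plan's own figure.** The plan states 80% power for 0.49 SD after attrition. Using d = (z_alpha + z_power) × √(2/n):

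- n = 51 per arm, one-sided 0.05: (1.645 + 0.842) × √(2/51) = 0.492. This reproduces.
- n = 51 per arm, two-sided 0.05: (1.960 + 0.842) × √(2/51) = 0.555, with power 69.7% at 0.49 SD.
- n = 64 per arm, two-sided 0.05: 0.495, but that is before attrition.

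Sidedness is not stated. The present point does not depend on it; 0.49 SD serves only as the assumed true effect below.

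**3. Effect of adjusting for antipsychotics.** The documents give neither a start rate nor a drug effect, so every input here apart from 0.49 SD, the sample sizes, about 20% attrition and the FFT share is assumed. Two simulations bracket the answer.

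*A. Single end-point regression.* 51 per arm; baseline score in both models (correlation 0.6 with outcome); starts driven by the interim score (log-odds 3 per SD); 3,000 runs; two-sided 0.05. Placebo starts range from 13% to 32%.

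| Antipsychotic effect | By assignment | Adjusted | Power by assignment | Power adjusted |
|---|---|---|---|---|
| none | 0.49 SD | 0.43 to 0.38 | 87% | 79% to 72% |
| 0.5 SD | 0.45 to 0.42 | 0.43 to 0.38 | 84% to 81% | 79% to 72% |

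With no drug effect the shift is 0.488 − 0.427 = 0.06 to 0.488 − 0.378 = 0.11 SD. With a 0.5 SD drug effect it is 0.453 − 0.427 = 0.03 to 0.420 − 0.378 = 0.04 SD. All shifts are downward.

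*B. Mixed model over visits 0 to 6 and 12 months.* Random intercept and slope; 128 patients; about 20% dropout; placebo antipsychotic use 22%; log-odds 1 or 2 per SD; Omega-3 effect held constant after month 6. Large-sample estimates at log-odds 2:

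| Scenario | Month 6: by assignment, adjusted | Month 12: by assignment, adjusted |
|---|---|---|
| Starts driven by underlying state, no drug effect | 0.483, 0.467 | 0.491, 0.459 |
| Starts driven by last score, 0.5 SD drug effect | 0.466, 0.484 | 0.457, 0.492 |

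The shifts are −0.016 and +0.018 SD at month 6, and −0.032 and +0.035 SD at month 12. At 10% use they stay within 0.01 and 0.02 SD. For scale, the standard errors at trial size are 0.15 and 0.19. The two models disagree on significance in 0.5–2.7% of trials at month 6 and 1.7–7.2% at month 12.

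**4. False positives with no Omega-3 effect**

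| Simulation | By assignment | Adjusted |
|---|---|---|
| A | 5.1–5.6% | 4.9–5.7% |
| B, month 12 | 4.0–5.7% | 4.3–6.1% |
| B, month 6 | 4.9–7.9% | 5.1–7.9% |

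The high month 6 rates affect both models alike. They arise because random coefficients do not fully match the assumed correlation, so the month 6 standard error and power in B are probably optimistic. Reporting whichever model is significant adds 0.1–1.3 points. Monte Carlo error in B is about 0.7 points.

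**5. Omitting the strata.** The expected FFT overlap is 0.33 × 0.25 × 128 = 10.6, about 11 patients. The antidepressant share and effect are assumed.

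- Milder case: 30% on antidepressants, a 0.3 SD difference at every visit. The SE changes by under 1%.
- Stronger case: 40%, with a further 0.5 SD difference in change. Month 12 SE is 0.199 without the strata and 0.190 with them (0.199/0.190 = 1.047), and power is 67% and 71%. Month 6 SE is 0.156 and 0.150 (ratio 1.04), and power is 86% and 87%.

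**The case against.** The plan already leans towards a by-assignment main analysis. The only firm wording is treatment and site, the antipsychotic sentence sits in a description of what mixed models can do, and the Hypotheses section speaks of randomised groups. On that view only a label is missing. The lean is real, but no sentence settles the matter, and the permitted alternative answers a different question.

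A reader might infer that the plan commits to adjusting for antipsychotics, or that it rules the strata out. Neither is supported: the first is permission, and the covariate list is open. A reader might also take all on-study use to be first use after randomisation. The exclusion covers only the previous month, so some starts may be restarts. The covariate is still a post-randomisation one.

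It is fair to say that the size is unsettled. Simulation A finds only attenuation, up to 0.11 SD; simulation B finds small shifts in both directions. Neither start rate comes from the documents: the 22% in B equals the plan's placebo conversion rate, which is a different quantity. Holding the effect constant after month 6 is also an assumption, since study capsules stop then. These limits weaken any single figure, not the point that the estimand changes.

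The strata half is the lesser one. The stronger case needs a difference in change between antidepressant users and non-users as large as the treatment effect the trial is powered for, and FFT involves few patients.

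**Conclusion.** The point holds at low severity, for the secondary and tertiary outcomes only. A model conditioned on antipsychotics started on study does not estimate the contrast in the Hypotheses section. The resulting shift in a 0.49 SD effect could be near zero or about 0.1 SD, depending on the start rate, how strongly symptoms drive starting, and the drug effect, none of which the documents supply. Naming the strata brings a small gain, from under 1% to about 5% of the SE, depending on how prognostic antidepressant status is.

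Two stronger conclusions are tempting and not supported. One is that adjustment inflates false positives: no inflation from adjustment alone was found, and the cost of choosing between models after the fact is about one point at most. The other is that the primary result is at risk: the antipsychotic sentence belongs to the mixed models, not to the survival analysis of conversion.

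**What to change.** In Power Calculations and Statistical Analyses, state that:

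- the main secondary and tertiary models compare assigned arms at months 6 and 12, adjusted for site, baseline score, antidepressant status and FFT participation;
- all scores are used regardless of whether an antipsychotic was started;
- any model adjusted for on-study antipsychotics is a sensitivity analysis with a different estimand;
- antipsychotic starts are reported by arm.

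The cost is wording and two covariates known at randomisation. Concomitant treatment is already recorded, and item 7a of Protections Against Risk already keeps patients who develop a disorder in follow-up. The adjusted model remains available, and no clinical rule changes. The downside is that the by-assignment estimate includes any effect of antipsychotics started on study, which the text should acknowledge.
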